# B. Study Design and Statistical Analysis

This is a randomized-controlled prospective study designed to assess whether or not a behavioral treatment for cocaine abuse will improve adherence to HAART therapy. The primary outcome of this study is a comparison of adherence to the prescribed HAART regimen in the intervention arm versus the standard of care arm as measured by a standardized three day recall self-assessment questionnaire administered every two weeks throughout the study. The secondary outcomes include viral suppression to undetectable levels using the RT-PCR assay (Roche) of HIV-1 viral load after 4 months and magnitude of change in the log10 viral load from baseline to the 8-week visit. The endpoint of 4 months was chosen, as most individuals who achieve undetectable viral loads will have done so by this time point [1].

Once subjects are identified as cocaine users and express interest in treatment for cocaine abuse, they will be recruited, assessed to see if they fulfill all of the inclusion/exclusion criteria, consented and randomized to either the treatment/intervention arm or the standard of care arm. Randomization will be achieved by selecting an unlabeled sealed envelope from a box containing as many envelopes as potential subjects. Half of the envelopes will say "treatment arm" and half will say "standard of care". In this way, subjects will be randomized.

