Subjects in the standard of care arm of the study will be provided with a list of referrals for substance-abuse treatment including Narcotics Anonymous, individual psychotherapy and rehabilitation programs at the first visit. They will be asked to return once each week for the first 6 weeks of the protocol and then every 2 weeks for the remainder of the study period, which is a total of 4 months. At each of these visits, they will be asked to provide a urine sample that will be tested for cocaine. They will also complete the 3-day adherence questionnaire with one of the investigators every two weeks. These subjects will be provided with additional drug treatment information by the regular clinic social workers and medical practitioners only if they request it according to the current standard of care. At the end of the study, they will be asked which if any of the cocaine treatment resources they utilized. Also, on the last visit, they will complete the Marlowe-Crowne social desirability questionnaire to assess the truthfulness of their self-reported data as compared to the treatment group.

Subjects in the treatment group will have the same number of visits with the same frequency as the standard of care arm, but in addition to providing urine samples every week and completing the adherence questionnaires every two weeks, they will be asked to attend to a 45 minute session at every visit with a trained addiction professional for a session of cognitive behavioral therapy specifically designed to address relapse prevention and coping skills training. Like the standard of care arm, they will be assessed with the Marlowe-Crowne at the last visit and asked about any other addiction treatments they utilized during the study period.

182 subjects will be enrolled in this study, with half participating in each of the two arms. This number will provide enough power to analyze the primary and secondary study outcomes as described below.

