The primary outcome variable is percentage of total prescribed medication doses taken as assessed by a 3 day self-report adherence questionnaire. The percentage of total prescribed doses taken will be compared in the two arms with a  $X^2$  test. Prior studies of non-drug abusers have shown that most patients report approximately a 70-80% adherence rate over the week prior to questioning with a standard deviation of around 20[8]. This self-reported adherence rate correlates with an actual adherence rate of around 55% as measured by microelectronic monitoring systems [8]. In other words, patients usually over report adherence by approximately 15-20% in a reproducible manner that still predicts changes in viral load. There is little data looking at self-reported adherence in a drug abusing population. One study has shown however that 32% of drug users obtain a viral load <400 copies/ml compared to 45% of non-users. The approximately 45% virologic response in non-users in this study is similar to the electronically monitored compliance of 55% in the previous study [7]. The lessened virologic response may be a result of pharmocokinetics and pharmocodynamics as well as viral resistance. Therefore, based on prior studies, non-users of drugs are likely to self-report around 70% adherence. Given, the lack of significant data on active drug abusers, 50% self-reported adherence is a reasonable estimate. To detect this difference, 17 subjects in each group are required.

To detect a  $0.9 \log_{10}$  difference in change in HIV-1 RNA viral load at 8 weeks (the time interval it takes to detect a  $1 \log_{10}$  change in viral load according to national guidelines) between groups assuming a standard deviation of 1.5 by unpaired t-test, a sample size of 45 subjects in each arm is required. Change in viral load is defined as the difference in  $\log_{10}$  copies/ml between the value measured at the time of the initial visit and the value at the 8-week visit. In a study comparing drug users and non-users, a  $0.9 \log_{10}$  difference was detected ( $0.8 \log_{10}$  change in the drug users and a  $1.7 \log_{10}$  change in the non-users) [7].

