To compare the proportion of subjects who obtain undetectable HIV-1 RNA viral loads at 16 weeks in the two arms a  $X^2$  test will be performed. In order to have power to detect a 20% difference between groups, assuming 40% will achieve undetectable levels in treatment arm and 20% will achieve undetectable levels in the standard of care arm, 91 subjects are required in each group.

Multiple linear regression analysis of the data will be performed to correlate adherence with other variables including age, gender, ethnicity, percentage of urine samples positive for cocaine during the study, utilization of alternate treatment modalities, and other variables shown to affect adherence in other research such as drug side effects or not being able to meet food and water requirements of the regimen [8b].

Data will be analyzed by an intention to treat analysis.

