# G. Study Subjects

In order to be included in this study, the patient must meet the following inclusion criteria:

- 1) Have documentation of HIV-1 positive status
- 2) Have a positive score on the Drug Abuse Screening Test (DAST)
- 3) Use cocaine regularly and more often than any other drug or alcohol
- 4) Express an interest in stopping their cocaine use
- 5) Must not be currently taking antiretroviral therapy
- 6) Have a viral load >55,000 copies/ml and a CD4 count < 200; thereby placing the subject in a category that should definitely receive therapy according to national guidelines [8b]. Treatment at higher CD4 loads and lower viral loads has still not been shown to affect clinical outcomes of time to disease progression and given the likelihood of non-adherence in drug-abusing populations is higher than in the general population, it may be unethical to start people on HAART when there are uncertain recommendations at present.

If a subject meets any of the following exclusion criteria, they will not be allowed to participate in the study:

- 1) On any form of antiretroviral therapy within the 4 months prior to the study
- 2) Exhibiting signs of physical dependence on any drug other than cocaine
- 3) Living in a facility where medicines are dispensed for them
- 4) Unable to give informed consent

Subject participation will not be limited on the basis of gender or race. Based on population of the community in which the study is to take place, Caucasian, Latino and African-American subjects will be primarily recruited. It is likely that slightly more men will be included in men as there are a larger proportion of male drug abusers in the general population.

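### The week-8 change in viral load is compared by an unadjusted t-test although baseline viral load is measured; use ANCOVA, with a censored regression as sensitivity analysis

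*Protocol*

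**What the plan says.** All of this is in the protocol; the SAP is not available.

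- Section B lists, as a secondary outcome, the "magnitude of change in the log10 viral load from baseline to the 8-week visit".
- It defines change as the difference in log10 copies/ml "between the value measured at the time of the initial visit and the value at the 8-week visit". A baseline value is therefore planned for every subject.
- It plans for a 0.9 log10 "difference in change in HIV-1 RNA viral load at 8 weeks" "between groups assuming a standard deviation of 1.5 by unpaired t-test, a sample size of 45 subjects in each arm is required". This is the only test named for the endpoint. The 0.9 comes from a cited cohort of drug users and non-users, with falls of 0.8 and 1.7 log10.
- The one regression in section B models adherence, not viral load.
- On size: "182 subjects will be enrolled in this study, with half participating in each of the two arms".
- Section G, inclusion criterion 6: "Have a viral load >55,000 copies/ml and a CD4 count < 200".
- No assay limit is given for this trial, and no rule for week-8 results below it. The only threshold in the text, 400 copies/ml, belongs to the cited cohort. For week 16, section B plans on "assuming 40% will achieve undetectable levels in treatment arm and 20% will achieve undetectable levels in the standard of care arm", so below-limit results are expected.

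**The concern.** Two separate matters bear on the named test.

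**Unused baseline.** A change-score t-test fixes the coefficient of week-8 on baseline log10 viral load at 1. If the true slope differs from 1, part of the variation in change is predictable from baseline and is left in the error term. ANCOVA estimates the slope instead.

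**Assay floor.** A fall can be recorded only down to the assay limit. Subjects enter above 55,000 copies/ml, and the planning values are mean falls of 0.8 and 1.7 with an SD of 1.5. Some true falls would therefore exceed what can be recorded, and more of them in the arm that does better. If below-limit results are entered as exact values, the arm difference is understated. That matters for an outcome that is a magnitude.

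**Working it through.** **1. The plan's own figure.** Alpha and power are not stated; assume two-sided 5% and 80%. The standardised difference is 0.9/1.5 = 0.6. The normal formula 2(1.960 + 0.842)²/0.6² gives about 44 per arm. The exact t solution is 44.6, rounded up to 45. The stated 45 reproduces.

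At the enrolled 91 per arm, power for 0.9 is 98.1%. The difference detectable with 80% power is (1.960 + 0.842) × 1.5 × √(2/91) = 0.62 log10.

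**2. Gain from baseline adjustment.** Hold SD(change) at 1.5. Let s0 be the baseline SD, s1 the week-8 SD and r their correlation; s0 and r are assumptions.

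- Solve s0² + s1² − 2·r·s0·s1 = 2.25, so s1 = r·s0 + √(r²s0² − s0² + 2.25).
- The ANCOVA residual SD is s1·√(1 − r²). The slope of week-8 on baseline is r·s1/s0.

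| s0 | r | s1 | slope | residual SD | variance reduction | n per arm, 80% power (exact t) |
|---|---|---|---|---|---|---|
| 0.3 | 0 | 1.470 | 0.00 | 1.470 | 4% | 42.8 |
| 0.3 | 0.2 | 1.531 | 1.02 | 1.500 | 0% | 44.6 |
| 0.4 | 0 | 1.446 | 0.00 | 1.446 | 7% | 41.5 |
| 0.5 | 0 | 1.414 | 0.00 | 1.414 | 11% | 39.7 |
| 0.5 | 0.1 | 1.465 | 0.29 | 1.458 | 6% | 42.2 |
| 0.5 | 0.3 | 1.572 | 0.94 | 1.500 | 0% | 44.6 |

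Over s0 = 0.3 to 0.5 and r = 0 to 0.3 the reduction is 0 to 11%, and it vanishes when the slope is near 1. A more favourable case, s0 = 0.7 and r = 0, gives 22%. At 91 per arm, power moves from 98.1% to at most 99.0% in the main range (99.5% in the favourable case).

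**3. The floor.** log10(55,000) = 4.74. To an assumed 400-copy limit (2.60) the largest recordable fall from the entry threshold is 4.74 − 2.60 = 2.14 log10. To an assumed 50-copy limit (1.70) it is 3.04. Subjects who enter higher have more room.

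**4. Effect of entering the limit as an exact value.** Simulation assumptions: baseline is 4.74 plus a half-normal with scale 0.3 to 0.6; latent mean falls are 0.8 and 1.7 with SD 1.5, so the true difference is 0.90; the week-8-on-baseline slope is 1 or 0.

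- 400 copies: about 10 to 15% against 26 to 33% of subjects are below the limit. The t-test estimates about 0.69 to 0.76.
- 50 copies: about 3 to 5% against 11 to 15%. The t-test estimates about 0.82 to 0.84.

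The methods were compared at scale 0.6, with 91 per arm and 500 runs per scenario:

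| Limit | t-test estimate | ANCOVA estimate | Tobit estimate | SE, t-test | SE, Tobit |
|---|---|---|---|---|---|
| 400 | 0.72–0.76 | 0.72–0.76 | 0.89–0.91 | 0.188 | 0.215–0.234 |
| 50 | 0.83–0.84 | 0.83–0.84 | 0.90 | 0.204–0.205 | 0.214–0.223 |

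The Tobit SE is larger by 5% (0.214/0.204) to 24% (0.234/0.188). Power is 97 to 98% for the t-test and 97 to 99% for Tobit. With no true difference, rejection rates were 4.4 to 6.4% across all three methods, which is near 5% given 500 runs.

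**The case against.** The strongest reply is that an unpaired t-test on change between randomised arms is valid, that its sample size is right, and that covariates and below-limit rules are ordinary SAP content. The endpoint needs 45 per arm and gets 91, so little power is at stake. All of that stands except one part: the protocol does name a test here, so proposing a better one is not a complaint about missing detail.

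It also stands that the floor is conditional. The protocol does not say that undetectable results are treated as exact values; it gives neither a limit nor a substitution rule. The 0.8 and 1.7 were observed in a cohort that reports suppression below 400 copies/ml, so they may already be floored. In that case the simulation counts the attenuation twice, and this cannot be checked from the documents.

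Four stronger readings are tempting and are not supported:

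- *Adjustment and censoring together gain precision at no cost.* They do different jobs. ANCOVA alone leaves the attenuation. The censored model removes it with a larger SE, needs a normal latent distribution with constant variance, and estimates a latent rather than an observed mean change.
- *The gain could reach 25%, worth 91/(1 − 0.5²) = 121 subjects per arm.* This needs a correlation of 0.5 between baseline and change. A half-normal baseline of scale 0.6 has SD 0.36, so the slope would have to be 0.5 × 1.5/0.36 = 2.1 log10 more fall per log10 of baseline. Entry above 55,000 copies/ml narrows the baseline range and makes this implausible.
- *Chance baseline imbalance biases the comparison.* Under randomisation it is random error, already within the t-test's standard error.
- *Week-16 suppression needs a baseline-adjusted logistic model too.* Nothing in this point concerns that endpoint.

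**Conclusion.** The point holds as a modest improvement to a stated secondary analysis. It is not an error in any figure. The named t-test leaves a measured covariate unused, and ANCOVA is asymptotically at least as precise. The variance reduction of about 0 to 11% rests on the assumed baseline SD and correlation and on the protocol's SD of 1.5.

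The floor is a risk to the size of the estimate and not to type I error. Its extent depends on the assay limit, on substitution at that limit, on the assumed baseline spread, and on the planning means being unfloored. Because it is conditional, and because the censored model has its own price, that model belongs in a sensitivity analysis and should not be the main one.

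**What to change.** In section B, keep the sample-size calculation and add analysis wording along these lines:

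> Week-8 log10 viral load will be compared between arms by analysis of covariance with terms for arm and baseline log10 viral load. The assay's lower limit, and the value entered for results below it, will be stated before any outcome data are compared by arm. As a sensitivity analysis, the same model will be fitted as a censored (Tobit) regression with week-8 values below the limit left-censored.

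The unpaired t-test may be reported alongside for continuity with the sample-size calculation.

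The cost is a few sentences: no extra visits, assays or subjects. The sensitivity analysis should be read with its wider standard error and its latent-normality assumption in mind.

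### The adherence regression names two post-randomisation predictors likely to differ by arm but not randomised arm, so their coefficients can pick up any CBT effect that bypasses measured cocaine use

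*Protocol*

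**What the plan says.** The last part of Protocol section B (Study Design and Statistical Analysis) describes the model: "Multiple linear regression analysis of the data will be performed to correlate adherence with other variables including age, gender, ethnicity". The list goes on with "percentage of urine samples positive for cocaine during the study, utilization of alternate treatment modalities" and closes with "other variables shown to affect adherence in other research such as drug side effects" or trouble meeting a regimen's food and water requirements. Randomised arm does not appear, and nothing says that the arms are modelled separately. The list is introduced as examples, so it is not exhaustive.

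Three other statements in the Protocol bear on this:
- Section A gives the rationale: helping patients stop using drugs is expected to improve adherence. Cocaine use is therefore the intended route of the CBT effect.
- Section B describes a referral list for the control arm: "Subjects in the standard of care arm of the study will be provided with a list of referrals for substance-abuse treatment". The other arm gets a CBT session at every visit. Both arms are asked at the end about other addiction treatment they used.
- The randomised comparison of adherence is a separate two-arm test in section B. The regression is neither the primary nor a secondary outcome.

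**The concern.** Arm is meant to change adherence. It is also likely to change two of the named predictors: CBT aims to lower the share of positive urines, and controls are pointed to outside treatment while the other arm already has therapy. Both predictors would then be lower under CBT. A variable that affects the outcome and also shifts the predictors should be in the model. Without it, the predictors' coefficients carry part of its effect.

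At stake is the reading of this secondary analysis. It could report that people who seek outside addiction treatment adhere less well, when they are simply more often controls. It could also credit cocaine use with benefit that came from therapist contact, general problem-solving skills or differences in reporting. This is the protocol's only stated analysis linking cocaine use to adherence, so its coefficients are likely to be read.

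**Working it through.** **Inputs from the Protocol (section B).** "182 subjects will be enrolled in this study, with half participating in each of the two arms", so 91 per arm. Adherence is given "with a standard deviation of around 20" points. The planned contrast is 70% v 50%, or 20 points: "To detect this difference, 17 subjects in each group are required".

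**The plan's own figures.** Alpha and power are not stated; I assumed two-sided 0.05 and 80%.
- 40% v 20% undetectable: n = [1.96√(2×0.3×0.7) + 0.842√(0.4×0.6 + 0.2×0.8)]² / 0.2² = 81.2. The continuity correction gives 90.9, so 91. Reproduced.
- 20 points with SD 20, t-test: 16.7, so 17. Reproduced.

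The document gives no figure for the regression itself.

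**Assumptions (not in the Protocol).** Positive urines are 25 points lower with CBT, with SD 35 within arm. Outside treatment is used by 40% of controls v 10% with CBT, or 30% v 15%. Neither predictor has an effect of its own. CBT has a direct effect τ on adherence. Within an arm the two predictors are independent.

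**Expected coefficients with both predictors fitted and arm left out.** They solve Sγ = τc, where S is the covariance matrix of the predictors over both arms and c holds their covariances with arm. At 40% v 10%:
- urine variance = 35² + 25²/4 = 1381.25
- uptake variance = 0.25×0.75 = 0.1875
- covariance = 0.25×25×0.30 = 1.875
- c = (−25/4, −0.30/4) = (−6.25, −0.075)
- determinant = 1381.25×0.1875 − 1.875² = 255.47
- outside treatment: τ × (−103.59 + 11.72)/255.47 = −0.360τ, or −7.2 points at τ = 20
- urines: τ × (−1.172 + 0.141)/255.47 = −0.00404τ per point, or −8.1 points over 0-100% at τ = 20

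At 30% v 15% the same steps give −3.8 and −8.8 points. At τ = 10 all four values halve.

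**False-positive rates at a nominal 5%, by simulation with both predictors fitted together:**

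| Direct CBT effect | Uptake, control v CBT | Outside treatment, no arm term | Urines, no arm term | Both, arm included |
|---|---|---|---|---|
| 20 points | 40% v 10% | about 47% | 46-50% | about 5% |
| 20 points | 30% v 15% | about 16% | 46-50% | about 5% |
| 10 points | 40% v 10% | about 18% | 16-18% | about 5% |
| 10 points | 30% v 15% | about 8% | 16-18% | about 5% |

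I repeated these with 6,000 trials per setting; results agreed to within about two percentage points.

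**Other gaps.** With urines 15 points lower (SD 30) and uptake 40% v 20%, the rates without arm are about 27% (urines) and 24% (outside treatment) at 20 points, about 10% each at 10 points, and 6-8% at 5 points. With a 30-point urine gap and uptake 50% v 10%, they are about 63% and 60% at 20 points.

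**When the problem disappears.** If CBT has no effect, or a predictor does not differ by arm, that predictor's rate stays at about 5%. If the whole CBT effect runs through cocaine use, outside treatment is significant in 4-5% of trials without an arm term, and the cocaine slope is the same with or without one (−0.50 in both models in one setting, −0.667 in both in another). That slope is then a real effect.

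**The case against.** **The omission is an inference.** The predictor list is open, and a full model is often fixed in an analysis plan, which is not shown here. A reader might infer that the protocol excludes arm and pools the arms unadjusted; it does not say so. What stands is narrower. The open part is limited to variables that other research has linked to adherence, which does not point to this trial's arm. Someone following the text as written would have no instruction to add it.

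**The protocol's own mechanism removes the bias.** A reader might infer that if CBT works as planned, outside treatment will look harmful. Under the rationale in section A the effect runs through cocaine use, and then there is no such tendency. This objection is correct and sets the condition on the point. But the protocol gives no ground for assuming full mediation. CBT adds 45 minutes of professional contact at each visit, and section C calls it a problem-solving process. The planned social-desirability scale shows that differential reporting is already a worry. A dip test is also a coarse measure: with full mediation but urine reliability of about 0.5 (uptake 40% v 10%, urine gap 25 points, SD 30), outside treatment came out at −4.1 points and was significant in 14% of trials.

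**The arm gaps are assumed.** This is true. The protocol gives no uptake or urine figures, and it does not say that the CBT arm is denied the referral list.

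**One-predictor figures are larger.** Fitting each predictor alone gives −8.0 points and 56% significant for outside treatment at 40% v 10%, 21% at 30% v 15%, and 52% for urines. The plan is a multiple regression, so those rates overstate the problem.

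**The consequence is limited.** The model only correlates variables, and the randomised comparison is a separate test. This stands in full.

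**Conclusion.** The point holds as a conditional one about a secondary analysis. The text names two predictors that arise after randomisation and are likely to differ by arm, and it does not name arm. If arm is left out and some of the CBT effect bypasses measured cocaine use, the two coefficients are biased downwards. Under the assumed gaps, the false-positive rate for outside treatment is about 8-18% at a 10-point direct effect and 16-47% at 20 points. For urines it is about 16-18% and 46-50%. It falls to the nominal 5% under full mediation through accurately measured cocaine use, or where there is no arm gap. An arm term restores about 5% in every setting where the predictor has no effect of its own.

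A reader might infer that the trial's main result is compromised. It is not: the primary comparison of adherence does not use this model. The point is minor.

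**What to change.** Name randomised arm as a fixed term in the multiple linear regression in Protocol section B. State that the coefficients for percentage of positive urines and for "utilization of alternate treatment modalities" are within-arm associations. Add that the arm coefficient from this model is adjusted for variables measured after randomisation, so the CBT effect on adherence is taken from the primary test.

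The cost is a sentence or two and one degree of freedom out of about 180. No new data are needed, and nothing is lost if the bias proves small.

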# Cognitive behavioral therapy for cocaine addiction to improve antiretroviral medication adherence in HIVpositive patients

# [name]

# A. Study Purpose and Rational

Many research studies have revealed that highly active antiretroviral therapy (HAART) improves HIV-related clinical outcomes, such as decreased opportunistic infections and prolonged survival as well as improves surrogate markers such as HIV viral load and CD4 cell counts [1,2]. Furthermore, optimal adherence to HAART regimens is necessary to obtain adequate viral suppression [3-5] and to avoid the emergence of viral resistance [6]. Patients who are actively abusing illicit drugs, including cocaine, have been shown to demonstrate decreased adherence to HAART as well as inferior virologic and immunologic responses to therapy as compared to both former and non-drug users [7]. Therefore, it is likely that helping these patients eliminate their illicit drug use may improve their adherence to HAART and their HIV clinical outcomes. The purpose of this study is to show that providing active cocaine abusers with cognitive behavioral therapy aimed at relapse prevention and coping skills training will increase their HAART regimen medication adherence as assessed by a self-adherence questionnaire over a 4 month period.

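### Cocaine use, the direct target of the therapy, is tested at every visit in both arms but is neither a named outcome nor compared between arms

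*Protocol*

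**What the plan says.** Protocol section A gives the causal argument: "it is likely that helping these patients eliminate their illicit drug use may improve their adherence to HAART".

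Section B sets out the measurements and outcomes:

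- **Cocaine measurement.** Of the standard of care arm it says: "At each of these visits, they will be asked to provide a urine sample that will be tested for cocaine". The treatment arm has the same visits and also gives urine samples. Section C confirms a urine dip test at every visit in both arms.
- **Primary outcome.** "The primary outcome of this study is a comparison of adherence to the prescribed HAART regimen".
- **Secondary outcomes.** "The secondary outcomes include viral suppression to undetectable levels using the RT-PCR assay (Roche) of HIV-1 viral load after 4 months". The other one named is how far log10 viral load has moved by week 8.
- **Use of the urine results.** A multiple linear regression is planned "to correlate adherence with other variables including age, gender, ethnicity", and the list continues with "percentage of urine samples positive for cocaine during the study, utilization of alternate treatment modalities", then side effects and food or water requirements. Study arm is not among the listed variables.
- **8-week viral load.** The arms are compared on the change from the initial visit: a 0.9 log10 difference "between groups assuming a standard deviation of 1.5 by unpaired t-test", 45 per arm.

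Sections B and F also plan to check whether social desirability scores are similar in the two arms. No section plans the same for cocaine use.

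**The concern.** The therapy acts on cocaine use. Adherence is expected to improve because cocaine use falls. The first step of that chain is measured repeatedly, by a test that does not depend on self-report, yet it is not analysed by arm.

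If adherence does not differ between arms, two explanations remain. CBT may not have reduced cocaine use in these patients, or it may have done so without helping adherence. The two point to different next studies, and the planned analyses do not separate them. If adherence does differ, the result cannot be tied to the route that the protocol proposes.

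The regression does not fill the gap. Urine results, use of other treatment and side effects all arise after randomisation, so their associations with adherence are not effects of CBT.

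**Working it through.** **1. Match each step of the argument to a planned analysis (section B).**

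| Step | Planned analysis | What it gives |
|---|---|---|
| CBT to cocaine use | none | nothing |
| Cocaine use to adherence | multiple linear regression | association only |
| CBT to adherence | chi-square test by arm | randomised comparison |
| CBT to viral load | t-test (8 weeks), chi-square test (16 weeks) | randomised comparisons |

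Only the first step has no analysis.

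**2. Data available.** Visits are weekly for 6 weeks, then every 2 weeks to 16 weeks. Taking the first visit as week 0, the later visits fall at weeks 1-6 (6 visits) and weeks 8, 10, 12, 14 and 16 (5 visits), 11 in all. With 182 patients, 11 x 182 = 2,002 scheduled tests. This count assumes full attendance.

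**3. What the comparison could detect.** Alpha and power are not stated. Two-sided 0.05 and 80% power are assumed; these reproduce the protocol's own sample sizes. For a per-patient percentage,

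detectable difference = (1.960 + 0.842) x SD x sqrt(2/91) = 0.415 x SD.

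The protocol gives no SD for this measure. For assumed SDs of 20, 30 and 40 points, the result is 8.3, 12.5 and 16.6 points.

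**4. The missed-sample rule matters.** With s scheduled samples, m missed and p positive, the percentage negative is (s - m - p)/s if missed samples count as positive, and (s - m - p)/(s - m) if only provided samples count. The two agree only when m = 0 or when no provided sample is negative. Section B does not say which denominator applies.

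**5. Baseline viral load in the 8-week comparison.** First, the stated figure: n = 2 x (1.960 + 0.842)^2 x (1.5/0.9)^2 = 43.6, so 44 per arm. The t-based calculation gives 44.6, so 45, as stated.

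For ANCOVA, hold the change SD at 1.5. Let b be the baseline SD, f the week-8 SD and r their correlation. Then f solves f^2 - 2rbf + b^2 = 2.25, and the ratio of ANCOVA to change-score variance is f^2(1 - r^2)/2.25. The values of b and r are assumed, because the protocol gives none:

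- b = 0.6, r = 0: f^2 = 2.25 - 0.36 = 1.89; ratio 1.89/2.25 = 0.84.
- b = 0.5, r = 0: f^2 = 2.25 - 0.25 = 2.00; ratio 0.89.
- b = 0.5, r = 0.3: f = 1.572, f^2 = 2.472; ratio 2.472 x 0.91/2.25 = 1.00.

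Over b = 0.3-0.6 and r = 0-0.5 the ratio runs from 0.84 to 1.00. If baseline and week-8 SDs were equal, the ratio would be (1 + r)/2 and the gain larger: 29, 33 or 38 per arm at r = 0.3, 0.5 or 0.7.

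The need is small in any case. At 91 per arm the unadjusted test has 0.9/(1.5 x sqrt(2/91)) = 4.05, and 4.05 - 1.96 = 2.09, which is 98% power.

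**The case against.** The strongest reply is that the trial asks whether CBT improves adherence, not how. An intention-to-treat comparison of adherence answers that whatever the route, and section C treats CBT's efficacy against cocaine addiction as established. This stands in part: the missing comparison invalidates no planned test and changes no sample size. But the review cited in section C covers all substances and compares with no treatment, whereas controls here receive treatment referrals. Efficacy in this setting should not be assumed. Only the protocol was available, but which outcomes are compared by arm is a protocol matter.

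Three stronger readings are tempting and are not supported:

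- **The regression removes the treatment effect by adjusting for the mediator.** That would need study arm in the model and its coefficient read as the CBT effect. Arm is not listed, the stated aim is correlation, and the arm comparison of adherence is a separate test. The list is open-ended, so a clarifying sentence is still useful.
- **Missed urine samples are dropped, so patients who stay away look cleaner.** The denominator is not defined, so this is a possibility and not something the protocol says. Counting missed samples as positive is not neutral either: it mixes attendance with use, and only the treatment arm has a 45-minute session at each visit.
- **Baseline viral load is ignored.** The 8-week outcome subtracts it. For adherence it is not the outcome's own baseline value. Only the 16-week chi-square test leaves it out, and randomisation keeps that test valid. Covariate adjustment is also commonly left to an SAP.

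**Conclusion.** The point holds for cocaine use. It is the therapy's direct target and the stated route to better adherence, and it is measured throughout in both arms. It is not a named outcome and is never compared by arm, so the trial as written cannot show whether CBT reduced it, and a null adherence result could not be attributed. This rests on reading the passages together, not on a wrong figure.

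The comparison is feasible at the planned size, on the assumed SDs. It would not prove mediation, since the link from cocaine use to adherence would remain an association, but it would tell a therapy that failed against cocaine from one that worked without changing adherence.

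The baseline viral load point is a minor precision matter. The planned t-test is valid, and the 0-16% variance reduction rests on assumed SDs and correlations.

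**What to change.** 1. Name as a secondary outcome the per-patient percentage of scheduled urine samples that are cocaine-negative, compared between arms. Count missed samples as positive, and add a sensitivity analysis on provided samples only, because attendance may differ by arm.
2. State that the regression on urine results, side effects and other treatment is descriptive and does not estimate the effect of CBT.
3. Optional: analyse week-8 log10 viral load by ANCOVA on arm and baseline log10 viral load, in place of the t-test on change.

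All the data are already to be collected, so only analysis wording changes. The costs are one more secondary outcome to report and some dependence of its result on the missed-sample convention, which the sensitivity analysis would show. The ANCOVA uses one extra degree of freedom.
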